4.9 Efficacy Evaluation

The co-primary efficacy endpoints are: “the change from baseline to the 1-week treatment in sputum viscosity score” and “the change from baseline to the 1-week treatment in expectoration difficulty score” and will be analyzed using the mITT and PP populations. The primary study objective will be assessed by testing superiority of NAC compared to placebo and will be achieved if at least one of the two co-primary end-points will be found statistically significant.

The key secondary objective will be assessed through the analysis of non-inferiority of NAC compared to ambroxol and, similarly, will be reached if at least one of the two co-

primary end-points will be found statistically significant for both the mITT and PP populations. Details will be found in section 4.9.1.4.

Conversely, the analyses of the remaining secondary efficacy endpoints will be treated as non-key secondary objectives since they will be performed only to support primary endpoints findings.

A by-subject listing of all efficacy variables (score of sputum viscosity, expectoration difficulty, sputum color and cough, and sputum volume) will be provided using the mITT population (Section 4.4.3).

4.9.1 Analysis and Data Conventions

This study is designed to test for the superiority of NAC vs. placebo and the non-inferiority of NAC vs. ambroxol hydrochloride in change from baseline to day 7 of sputum viscosity score as well as change from baseline to day 7 of expectoration difficulty score.

4.9.1.1 Multi-center Studies

A test of site-by-treatment interaction will be carried-out using a two-way nonparametric ANOVA. The interaction will be considered statistically significant for a two-tailed $\alpha=0.1$. Also, in order to graphically assess the possible heterogeneity of the treatment effect across centres, forest plots will be generated to display the results at each center. CCI

In the case of non-convergence or SAS errors/warnings in the log (due to low numbers of patients at some sites), sites with 8 or fewer subjects randomized will be grouped together.

4.9.1.2 Adjustments for Covariates

Adjustments for covariates will be performed for the following two parts.

First, for the two-way non-parametric ANOVA, modelling adjustments for covariates will be performed by including treatment, site, and site-by-treatment interaction terms in the model.

Secondly, adjustments of covariate for stratified Mann-Whitney U tests will also be performed by considering baseline score as a block/stratification variable in order to adjust imbalance. Block/stratification for baseline score refers to baseline results of sputum viscosity score, expectoration difficulty score, sputum color score, cough severity score and sputum volume. A new variable will be created dividing sputum volume into quartiles and this variable will be used as the block/stratification variable for baseline sputum score (as sputum score is a continuous measure unlike the other efficacy variables). Details of two-way non-parametric ANOVA can be seen in Appendix (Section 4.14.3).

4.9.1.3 Handling of Dropouts or Missing Data

Missing data on the primary and secondary efficacy endpoints will be imputed as treatment failures (MVTF) by replacing missing values using worst observation carried forward

(WOCF) with the worst scores recorded at baseline or post baseline (follow up) (including measurements from the premature discontinuation visit) imputed to missing visits. MVTF is the primary imputation method. The Expectation-Maximization (EM) algorithm and last observation carried forward (LOCF) will be used as sensitivity analyses. Data missing at baseline will not be imputed.

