- slow (at least 5 minutes) intravenous infusion of ambroxol hydrochloride 30 mg twice daily is superior to placebo in change from baseline to day 3 and to the end of 1-week treatment of sputum viscosity score or expectoration difficulty score and of other indicators of mucolytic activity: individual sputum viscosity and expectoration difficulty scores, cough score, mucous color score and mucous volume.

Safety objectives

- Confirm that 1-week treatment with iv NAC 600 mg twice daily is safe and well tolerated.

Design:

Multicenter, randomized, rater- and patient-blind, placebo- and active-controlled, 3-arm parallel group clinical trial.

Subjects will be randomized to NAC or ambroxol or placebo in a 1:1:1 ratio.

The study will consist of a total of 4 core hospital visits and a follow-up call 2 weeks after end of treatment. If the patient is still hospitalized or if more convenient for the patient, the follow-up phone call can be replaced by a follow-up hospital visit.

Number of patients: A total of 333 patients will be randomized. This number includes 10% overage to allow for patients who discontinue the trial prematurely ("drop-outs") without contributing to the primary endpoint.

Trial duration: Approximately 8 months. The enrolment period will be approximately 7 months.

Duration of patient participation: Up to 4 weeks. Each patient will undergo a screening period of up to 1 week, a 1-week treatment period and a 2-week follow-up period.

Participating Countries: China

Number of Sites: Approximately 25

Population: **Inclusion criteria**

Patients will be enrolled in the trial if all of the following criteria are met:

1. Male or female adult (≥ 18 years old) hospitalized patients with respiratory tract diseases and abnormal mucus secretions such as: acute bronchitis, chronic bronchitis and exacerbations, emphysema, mucoviscidosis and bronchiectasis. Diagnostic criteria for these conditions are provided in [Annex 1](#)
2. Chinese ethnicity and/or Chinese
3. Signed the informed consent form before any study-related procedure
4. Sputum viscosity score ≥ 2 at randomization visit
5. Expectoration difficulty score ≥ 2 at randomization visit
6. Willingness and ability to comply with study procedures

Exclusion criteria

Patients will not be enrolled if one or more of the following criteria are met:

1. Intolerance or contra-indication to treatment with NAC or ambroxol or allergy to any component of the study treatments

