20.4.4. HANDLING OF MISSING DATA

Missing data on the primary and secondary efficacy endpoints will be imputed as treatment failures (MVTF) by replacing missing values with the scores recorded at baseline or last measurement, whichever is worse as primary imputation method. Expectation-maximization (EM) algorithm and

last observation carried forward (LOCF) will also be used as sensitivity analyses. Details regarding the EM algorithm (i.e. the randomization seed and the SAS code that will be used) will be reported in the SAP.

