Amendment Final version	Oct.09 2019	PPD	Add modified MW test dummy code in the appendix Update concomitant medication partial date imputation Add additional section of Changes to protocol-defined analyses Add Hochberg procedure into Appendix. Remove TOC of CS in the SAP.

V2.0	April 13 2021	PPD	
Adjusted “change from baseline to 1-week treatment” to “change from baseline to day 7” for viscosity score, expectoration difficulty score sputum color score, cough severity score and sputum volume
 
Modified the partial date conventions for prior and concomitant medication.
 
Added summaries of Covid-19 to disposition, protocol deviations and adverse events sections.
 
Added definition and explanation of minor protocol deviations for morning dose between 9am and 11am, and efficacy assessments occurring within 2 hours after morning dose of study medication.
 
Added summary of major protocol deviations leading to exclusion from the Per-Protocol Population.
 
Defined prior prohibited medications and prohibited concomitant medications.
 
As sputum volume is a continuous measure, added new variable (sputum volume in quartiles) for the stratified Mann-Whitney U tests.
 
Adjusted the replicate number of bootstraps from 5000 to 1000.
 
Adjusted the code of two-way nonparametric ANOVA procedure in 4.14.3.
 
Adjusted the code of EM algorithm in 4.14.4.
 
Specified that assessments for the premature discontinuation visit are to be included for data imputation.
 
CCI
 
Clarified that missing baseline data will not be imputed.
 
Clarified that the the decision to proceed or not proceed to the second gate for the non-inferiority comparison (for both the mITT and PP Population) only depends on the superiority results for the mITT Population.
 
Explained the process for reporting Suspected, Unexpected Serious Adverse Reactions (SUSARs).
 
Added description of the baseline definition to allow efficacy assessments after and within 2h of first IMP to be used.
 
To further specify the number of multiple imputation of EM to 0 in SAS code as EM algorithms does not involve multiple imputation.
 
Clarified that fiberoptic bronchoscopies are collected as concomitant procedures, regardless of relationship to AEs and SAEs.

------	---------------	-----	---

TABLE OF CONTENTS

1	INTRODUCTION	9
2	STUDY OBJECTIVES	9
2.1	Primary objective	9
2.2	Secondary objectives	9
2.2.1	Efficacy objectives	9

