4.4.3 Modified Intention-To-Treat (mITT) Population

The Modified ITT (mITT) Population will comprise all subjects in the ITT population who received at least 1 dose or partial dose of the IMP.

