4.9.1.4 Multiple Comparisons/Multiplicity

The overall type I family-wise error rate will be preserved at the one-tailed 0.025 nominal level (i.e. $\alpha = 0.025$) by controlling multiplicity over the two co-primary endpoints and over the two study targets (superiority and non-inferiority) using a multiple-sequence gatekeeping procedure (Keays et al., 1991). To achieve this, the analyses on primary endpoints will be grouped into two family of comparisons (gatekeepers) and processed as follows:

1. The first gatekeeper includes the superiority contrasts “NAC vs placebo” with the adjustment for multiple comparisons across the two co-primary endpoints performed according to Bonferroni. This implies that a difference will be considered statistically significant for a one-tailed p-value ≤ 0.0125 (i.e. $\alpha/2 = 0.0125$).
The transition to the second gatekeeper requires that at least one of the two co-primary endpoints is statistically significant in the mITT population.
2. The second gatekeeper includes the family of non-inferiority contrasts “NAC vs ambroxol” conducted for both the mITT population and PP population.
The analyses in the second gatekeeper will be performed depending upon the results obtained in the first gatekeeper as shown below:
 - a. If both superiority contrasts are found statistically significant in the mITT population, non-inferiority will be tested on both co-primary endpoints for both the mITT and PP populations with an overall probability α set to 0.025 (one-tailed) and with the adjustment for multiple comparisons across the two co-primary endpoints performed according to Hochberg. Details of the Hochberg procedure can be found in Appendix (Section 4.14.1).
 - b. If only one of the two superiority contrasts are found statistically significant in the mITT population, non-inferiority will be tested for that co-primary endpoint only for both the mITT and PP populations and will be considered achieved if the associated one-tailed p-values are ≤ 0.0125 .

Statistically significant results will be needed in both the mITT and PP populations to accept the hypothesis of non-inferiority of NAC versus ambroxol.

Consistent with the hypothesis testing process performed on the co-primary endpoints, the strategy described above will also be applied to control the coverage of confidence intervals at the two-tailed 95% nominal level (i.e. $1 - 2\alpha = 0.95$).

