4.11 Determination of Sample Size

This study has been powered to reach statistical significance for the superiority comparisons of N-acetyl cysteine (NAC) vs. placebo (primary study objective), and for the non-inferiority comparisons of NAC vs. ambroxol hydrochloride (key secondary study objective) in at least one of the two co-primary endpoints at the end of the 1-week treatment. This implies that sample size computation must account for the type I error inflation caused by the multiplicity over the two co-primary endpoints and by the multiplicity over the study targets (superiority and non-inferiority assessments) as well as the logical relationships among the two family of hypotheses with the non-inferiority testable only provided that the superiority contrast, assessed on the same endpoint, is statistically significant. To accomplish this, a multiple-sequence gatekeeping procedure [21] was implemented in a Monte Carlo (MC) study with 1000 runs and with the Bonferroni correction applied to the set of superiority comparisons (first gatekeeper) and

the Hochberg correction applied to the set of non-inferiority comparisons (second gatekeeper) in order to control the overall type I family-wise error rate at the one-tailed 0.025 significance level. Details on the adopted gatekeeping strategy are reported further on.

For the superiority tests, and with group sample sizes of 100 patients in placebo group and 100 patients in NAC group, the Monte Carlo study estimated an overall power (“disjunctive” power) close to 93% to reach statistical significance in at least one co-primary end-point. These calculations are based on a one-sided Mann-Whitney test and assuming a minimal clinically relevant difference of 0.35 points between placebo and NAC on a 0-3-point scale, standard deviation equal to 0.79 and 0.77 for sputum viscosity and expectoration difficulty scores (change from baseline to the 1-week treatment) respectively and a correlation between the two end-points equal to 0.31.

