For the non-inferiority tests, a sample of 100 patients per each active treatment group ensures sufficient disjunctive power (Monte Carlo disjunctive power = 82%) to detect non-inferiority between NAC and ambroxol in at least one co-primary end-point. These calculations are based on a one-sided non-inferiority t-test assuming a margin of non-inferiority equal to 0.30, standard deviation equal to 0.79 and 0.77 for sputum viscosity and expectoration difficulty scores (change from baseline to the 1-week treatment) respectively and a correlation between the two endpoints equal to 0.31.

Assuming a drop-out rate of about 10% over one week of entry, a total of 333 patients will be randomized (i.e. 111 patients in the placebo group, 111 patients in the NAC group and 111 patients in the ambroxol group).

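### The EM sensitivity code in SAP 4.14.4 yields no imputed scores, and the powers in SAP 4.11 do not account for WOCF in mITT or the two-population NI rule

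*SAP*

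**What the plan says.** **EM sensitivity analysis.** Protocol 20.4.4 leaves the EM details to the SAP, including "the randomization seed and the SAS code that will be used". SAP 4.9.1.3 makes WOCF the primary imputation, "with the worst scores recorded at baseline or post baseline (follow up) (including measurements from the premature discontinuation visit) imputed to missing visits", and leaves a missing baseline unimputed. SAP 4.9.2 then calls for superiority and NI p-values after EM imputation, for both co-primary endpoints, in mITT and PP. The same is asked after LOCF.

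SAP 4.14.4 gives the code: PROC MI with `NIMPUTE=0`, the statement `EM OUTEM=<out_data>`, and `VAR spv epd spc cough sv`. It describes EM as estimating the means and covariance matrix of a multivariate normal, and then says how the imputed values are to be rounded and bounded. The V2.0 entry in the SAP version history gives the reason for the zero: "To further specify the number of multiple imputation of EM to 0 in SAS code as EM algorithms does not involve multiple imputation".

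**Power.** SAP 4.11 quotes about 93% for superiority "with group sample sizes of 100 patients in placebo group and 100 patients in NAC group", and says the same number in each active arm "ensures sufficient disjunctive power (Monte Carlo disjunctive power = 82%) to detect non-inferiority". Protocol section 3 explains the 10% overage as covering patients who leave early "without contributing to the primary endpoint". The primary set, mITT, is "all subjects in the ITT population who received at least 1 dose or partial dose of the IMP" (SAP 4.4.3). SAP 4.9.1.4 adds: "Statistically significant results will be needed in both the mITT and PP populations to accept the hypothesis of non-inferiority".

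**The concern.** The EM analysis is one of only two planned checks on an imputation that scores every leaver as unchanged or worse. If the printed code cannot deliver it, someone must choose the missing step and the model at analysis time, or LOCF is left as the sole check. The same gap affects the EM results listed for the secondary endpoints in SAP 4.9.3.

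On power, the sizing text treats drop-outs as adding nothing. The analysis text keeps a dosed leaver with a baseline score and gives that patient a change of zero or worse. Only patients never dosed, or with no baseline score, drop out of the calculation. The NI power also says nothing of having to pass in two populations. A reader will take 93% and 82% as the powers of the planned primary and key secondary analyses, and the text does not establish that.

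**Working it through.** **1. What the EM code delivers**

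- `NIMPUTE=0` asks for no imputed data sets, and `OUTEM=` stores parameter estimates. The SAP's own description (means and covariance matrix) agrees.
- The tests in SAP 4.14.5 and 4.14.6 need one change score per patient, and the rounding rule in 4.14.4 needs imputed scores to round. The code produces neither.
- The five `VAR` names are viscosity, difficulty, colour, cough and volume. No treatment, baseline or Day 3 term appears. If the five are Day 7 values, a leaver has all five missing, nothing is left to condition on, and EM could supply at best the mean pooled over all arms.
- Illustration, assuming that reading and 10% loss in every arm: a completer difference of 0.35 becomes 0.9 × 0.35 + 0.1 × 0 = 0.315.

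**2. Reproducing the stated powers**

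Inputs from SAP 4.11: 100 per arm, difference 0.35, SD 0.79 and 0.77, correlation 0.31, NI margin 0.30. From SAP 4.9.1.4: one-sided 0.0125 per endpoint for superiority; then Hochberg at 0.025 for NI if both pass, or 0.0125 on the one that passed. Assumed, because it is not stated: NAC and ambroxol are truly equal.

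- Per endpoint: Φ(0.35 / (SD × √(2/100)) − 2.241). Viscosity: 0.35/0.1117 = 3.13, giving 81.4%. Difficulty: 0.35/0.1089 = 3.21, giving 83.5%.
- At least one endpoint, correlation 0.31: 94.6% for a t-test and 93.6% after the Mann-Whitney efficiency 3/π. Simulation gives 93.4% to 93.6%. Stated: about 93%.
- NI after the superiority step, by simulation: 79.9% to 80.6%. Stated: 82%. The Monte Carlo standard error with 1,000 runs is √(0.82 × 0.18/1000) = 1.2 points.
- Overage: 100/0.9 = 111.1, against 111 per arm.

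Both figures therefore match, within simulation error, 100 contributing patients per arm and one NI analysis set.

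**3. Power under the planned handling, 111 per arm**

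The tests are those used for sizing (Mann-Whitney, NI t-test), with 20,000 runs. Leavers are set to a change of 0, the most favourable value WOCF allows. The placebo change is not in the documents, so a range is shown.

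| Assumption | Superiority | NI, mITT | NI, mITT and completers |
|---|---|---|---|
| 0.35 and SDs already on the imputed scale | 95.6% | 85.4% | not run |
| Completer scale, 11 per arm at 0, placebo change 0 | 92.9% | 84.7% | 79.6% |
| same, placebo change -0.3 | 92.3% | 83.4% | 79.4% |
| same, placebo change -0.65 | 90.5% | 79.7% | 77.3% |
| same, placebo change -1.0 | 88.7% | 76.2% | 76.1% |

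In the completer rows the mean difference is (100/111) × 0.35 = 0.315. Power falls down the column because leavers at 0 sit further from the completers and widen the spread. For viscosity in the NAC arm the variance is 0.901 × 0.79² + 0.901 × 0.099 × μ², where μ is the NAC completer change. The SD is 0.76 at μ = -0.35 and 0.85 at μ = -1.35.

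If loss is a 10% chance per patient rather than exactly 11 per arm, the ranges across the same placebo changes are 92.3% to 85.1% for superiority, 83.9% to 71.9% for NI in mITT and 78.6% to 68.9% jointly (10,000 runs).

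**4. Check with the planned tests**

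Stratified test for superiority, modified Wilcoxon-Mann-Whitney for NI, integer 0-3 scores, 40% assumed to have baseline 3, 10,000 runs, placebo change -0.3 / -0.65 / -1.0. With 100 per arm and no loss: 94.8 / 94.4 / 94.2% superiority and 82.5 / 82.2 / 82.0% NI. With 111 per arm and 11 set to 0: 94.5 / 92.0 / 89.4% and 85.9 / 82.2 / 77.2% (mITT only; no joint figure was run).

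**The case against.** **On EM.** This is a sensitivity analysis, its intent is plain from the rounding rule, and one output option supplies the data set. What the `VAR` names hold is not fully stated, so the pooled-mean result is conditional, and running EM by treatment with Day 3 is a modelling choice. All of that is fair and limits the point. It does not remove it: the protocol sends readers to the SAP for the code that will be used, the zero was set deliberately in V2.0, and that code cannot yield the required p-values.

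**On power.** SAP 4.11 never says that 0.35 and the SDs exclude imputed failures. If they are on the imputed scale, the stated powers are conservative. With the planned tests and exactly 11 leavers per arm at 0, power in mITT is close to or above the stated values at placebo changes of -0.3 and -0.65. NI will be judged on its p-value and confidence limit, not against 82%. These arguments stand. A reader might infer that the stated powers definitely exclude imputed scores, or that the trial is underpowered. The documents support neither, because they omit the inputs that decide it.

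**Other inferences that do not hold.** The seed in the EM code is a placeholder, but EM estimation makes no random draw, so no result depends on it. SAP 4.4.5 and 4.10.1 leave open whether early leavers are in PP, but SAP 4.3.2 refers exclusions to the Protocol Deviation Specification, which is not among these documents and may settle it. An extra PP analysis on observed Day 7 scores would be a preference, not a correction.

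**Conclusion.** The EM code is wrong as written. It gives no completed scores, so the EM p-values in SAP 4.9.2 cannot be produced from it, and LOCF is the only executable check on WOCF. This rests on the SAP text and the meaning of two SAS options, and on no numerical assumption. The primary result is not affected.

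The power statement is incomplete rather than wrong. It fits 100 contributing patients per arm and one NI set, and does not account for WOCF in mITT or for the joint NI requirement. Actual power could be above the stated values (about 96% and 85%) or below them. On the completer reading with 11 leavers per arm at 0 and placebo change 0 to -1.0, the sizing tests give about 93% to 89% for superiority. Joint NI is then about 80% to 76% if PP is completers only. If leavers stay in PP and nobody else is excluded, joint NI equals the mITT figure, about 85% to 76%. All of these assume equal loss across arms and NAC equal to ambroxol. The point is worth acting on but not critical.

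**What to change.** **SAP 4.14.4.** Run EM by treatment on the baseline, Day 3 and Day 7 scores and write the completed data with `EM OUT=`. Then round and truncate as 4.14.4 already states, and set any filled-in baseline back to missing, as 4.9.1.3 requires. `NIMPUTE=0` can stay. The cost is a few lines of code, and the protocol already leaves EM details to the SAP. The drawback is that single EM values are treated as observed, so these p-values are somewhat optimistic and should be labelled supportive.

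**SAP 4.11.** Restate superiority and NI power for mITT with WOCF at 111 per arm, and NI power for the joint mITT and PP requirement. State the placebo change, the loss per arm, and whether 0.35 and the SDs describe completers or imputed data. The cost is one rerun of the existing Monte Carlo and some wording; the restated figures may be less favourable.

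No test, population, primary imputation or sample size changes.
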